The study will be conducted in compliance with procedures outlined in this protocol, ICH harmonised tripartite guidelines for good clinical practice, the Declaration of Helsinki and with laws of Bangladesh.

Research Design and Methods

Describe in detail the methods and procedures that will be used to accomplish the objectives and specific aims of the project. Discuss the alternative methods that are available and justify the use of the method proposed in the study. Justify the scientific validity of the methodological approach (biomedical, social, or environmental) as an investigation tool to achieve the specific aims. Discuss the limitations and difficulties of the proposed procedures and sufficiently justify the use of them. Discuss the ethical issues related to biomedical and social research for employing special procedures, such as invasive procedures in sick children, use of isotopes or any other hazardous materials, or social questionnaires relating to individual privacy. Point out safety procedures to be observed for protection of individuals during any situations or materials that may be injurious to human health. The methodology section should be sufficiently descriptive to allow the reviewers to make valid and unambiguous assessment of the project. (DO NOT EXCEED TEN PAGES, USE CONTINUATION SHEETS).

This is a phase III, randomised, partially-blinded, placebo-controlled, multicentre outpatient study to assess the safety, tolerability and immunogenicity of Influenza Virus Vaccine, trivalent, Types A & B, Live Cold-Adapted (CAIV-T) administered concomitantly with live, attenuated, orally administered poliovirus vaccine (OPV) to 2400 healthy children aged 6 to less than 36 months. Informed consent will be sought from all parent(s)/legal guardian(s) of children before any study-related procedures are performed.

Subjects will be prospectively randomised to one of three study groups in a 1:1:1 ratio as detailed below:

Study Group	No. of Subjects	Dose 1	Dose 2
1	800	CAIV-T (IN) OPV	CAIV-T (IN)
2	800	Placebo (IN) OPV	Placebo (IN)
3	800	CAIV-T (IN)	CAIV-T (IN)

CAIV-T = influenza virus vaccine, trivalent, types A and B, live, cold-adapted;

OPV = live, attenuated, trivalent, poliovirus vaccine, administered orally;

Placebo = placebo consisting of saline only

IN = intranasal

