Adverse events will be monitored for 11 days following receipt of each dose of study vaccine. FRAs making daily home visits, as described above, will collect information on adverse events for all subjects. In addition, parent(s)/legal guardian(s) will be instructed to notify the Investigator should the subject develop any clinically significant illness or event, including but not limited to those requiring an unscheduled healthcare provider visit or prescription/non-prescription medications within 11 days (Days 0 to 10) of vaccination. All serious adverse events (SAEs) will be monitored from study enrolment to study completion. Details of the event, including concomitant medication(s) and treatment will be recorded on the SAE form provided.

If a subject terminates from the study due to an adverse event, the Investigator will report this to the Sponsor's pharmacovigilance group or designee, within 24 hours of learning of termination, by faxing the completed, signed and dated Subject Outcome page of the Case Report Form (CRF).

Table 3 summarises the study procedures for all subjects participating in the study. In order that study visits are scheduled within the correct timeframes, the day of study vaccination visit should be considered as Day 0.

Table 3

SCHEDULE OF PROCEDURES

Study Visits	1			2			3	
Visit Window (Days After Previous Visit)	(0)	(2-4)	(10-12)	(35±7)	(0)	(2-4)	(10-12)	(35±7)
Informed Consent	X							
Subject Eligibility	X							
Demography	X							
Medical History	X			◆				◆
Physical Examination	X							
Blood Sample	X			X				X
Vaccination	X			X				
Assess Acute Reactions – 15 Minutes Post Vaccination	X			X				
Daily home visits for complications and SAEs		X	X		X	X		
Review of Morbidity Data				X				X
Record Concomitant Medication Use	X			X				X
*Adverse Event Collection	X	X	X	X	X	X	X	X
Serious Adverse Event Reporting	X	X	X	X	X	X	X	X

Randomisation Procedures

A randomisation schedule will be prepared and provided by WLW or by their designate. Study participants will be prospectively randomised in a 1:1:1 proportion among Study Group 1, Study Group 2, and Study Group 3. See group distributions in Section 3.1.3. Once a subject number and/or treatment is assigned to a particular subject, it will not be reused, even if the subjects drops out of the study prior to administration of the first study vaccination.

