The multidimensional comparison of primary interest is (1) to evaluate non-inferiority of the serum antibody response to OPV following concomitant administration with CAIV-T relative to the response to OPV administered separately temporally (at least 1 month apart) from CAIV-T and (2) to evaluate non-inferiority of the serum antibody response to CAIV-T following concomitant administration with OPV relative to the immune response of CAIV-T administered separately temporally (at least 1 month apart) from OPV. The response criterion for each viral strain of CAIV-T is a four-fold increase from baseline titre in the hemagglutination inhibition assay (HAI) for influenza virus strains A/H3N2, A/H1N1, and B. The response criterion for each antigen component of OPV is a post-vaccination titre of 1:10 for Poliovirus types 1, 2, and 3 by virus neutralisation assay. The primary analysis interval for influenza strains A/H1N1, A/H3N2, and B is one month following the second intranasal vaccination. The primary analysis interval for poliovirus types 1, 2, and 3 is one month following the single dose of OPV. The primary analysis endpoint will be achieved if lower limits of six independent 95% one-sided confidence intervals for differences in response rates are each greater than -10%.

It is expected that approximately 2,400 subjects will be enrolled in at multiple study sites. Determination of the appropriate sample for this study is dependent on the following assumptions:

-- Loss to follow-up is not greater than 15%.

-- Post-dose 2 influenza antibody response rates, measured as a four-fold or greater increase from baseline serum hemagglutination assay (HAI) will be similar to those observed in earlier studies of CAIV- T, ranging from 48% to 68% for the three strains □ Immune response rates for OPV measured at the end of the study by 1:10 or greater

virus neutralisation assay titres for Poliovirus types 1, 2, and 3 will be similar to those observed in earlier studies of OPV and may be as low as 75%.^{32,36}

-- The co-administration of CAIV-T with OPV will be demonstrated not to interfere with immune response to poliovirus and co-administration of OPV with CAIV-T will be demonstrated not to interfere with immune response to CAIV-T if each lower bound of 95% one-sided confidence intervals for the Poliovirus type 1, Poliovirus type 2, and

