Poliovirus type 3 response rates compared between Study Group 1 and Study Group 2 AND each lower bound of 95% one-sided confidence intervals for the A/H1N1, A/H3N2, and B response rates after 2 doses compared between Study Group 1 and Study Group 3 is greater than -10%. A study with at least 680 subjects completed in each treatment group would provide 98% power to demonstrate that a treatment with a true response rate of 55%, is non-inferior to a reference treatment with a true response rate of 55%, on a 10% criterion for non-inferiority. The simultaneous evaluation of six independent comparisons, each with 98% probability of success, provides an overall probability of success greater than 90%. The planned enrolment will provide at least 90% power to demonstrate non-inferiority of co-administration compared to separate administrations (at least one month apart) of liquid CAIV-T and OPV based on response criteria for antibody levels to three polio antigens and three influenza virus strains.

The proportion of responders for concomitant administration of CAIV-T and OPV

(Group 1) will be compared with the immune response to polio antigens in Group 2 and the immune response to influenza antigens in Group 3. The non-inferiority evaluation will be based on exact 90% two-sided confidence intervals for the six differences in proportions . If the lower limit of the confidence interval ** of $\frac{\text{co-admin}}{\text{reference}}$ is $\geq -10\%$ for polio antigen Types 1, 2, and 3 and for influenza strains A/H1N1, A/H3N2 and B, then the null hypothesis of inferiority with respect to a 10% criterion will be rejected at $\alpha=0.05$. StatXact will be used to determine the exact confidence interval. In a secondary analysis the comparison between co-administration and separate administration regimens will be based on the antibody titre (polio) or the titre ratio to baseline (influenza) expressed on a logarithmic scale. The t-test of the mean difference (in log) will be used to form the 90% confidence interval. The estimated difference and the confidence interval will then be exponentiated to obtain the GMT (geometric mean titre, polio) or GMR (geometric mean ratio, influenza) ratio (co-admin./reference) and its 90% confidence interval. If the lower limit of each confidence interval is ≥ 0.5 , the null hypothesis of inferiority with respect to a two-fold criterion will be rejected at $\alpha=0.05$.

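### The overall-power sentence is arithmetically wrong: six independent comparisons at 98% each give 88.6%, not more than 90%

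*Protocol*

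**What the plan says.** The study-group table in Research Design and Methods sets three groups of 800: Group 1 receives CAIV-T with OPV, Group 2 placebo with OPV, Group 3 CAIV-T alone. The ratio is stated there ("Subjects will be prospectively randomised to one of three study groups in a 1:1:1 ratio as detailed below") and again under Randomisation Procedures ("Study participants will be prospectively randomised in a 1:1:1 proportion among Study Group 1, Study Group 2, and Study Group 3").

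Data Analysis sets out the primary comparisons and the power:

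- Group 1 "will be compared with the immune response to polio antigens in Group 2 and the immune response to influenza antigens in Group 3". That makes three polio and three influenza comparisons, and all six must succeed.
- The margin is 10 percentage points, each comparison is tested at 0.05, and "The non-inferiority evaluation will be based on exact 90% two-sided confidence intervals for the six differences in proportions".
- Planning inputs: "It is expected that approximately 2,400 subjects will be enrolled in at multiple study sites"; "Loss to follow-up is not greater than 15" percent; influenza response between 48% and 68%; polio response possibly as low as 75%.
- With at least 680 completers per group and a true response of 55% in both arms, power is given as 98% "on a 10% criterion for non-inferiority".
- Six independent comparisons, each at 98%, are then said to be enough: this "provides an overall probability of success greater than 90" percent.
- The paragraph ends by claiming at least 90% power for the planned enrolment.

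**The concern.** Success requires all six lower limits to clear the margin, so the power that matters is the joint power. The protocol obtains it by treating the six comparisons as independent, which means multiplying six probabilities. The figure it reports is higher than that product.

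Two things are at stake. First, an ethics committee or sponsor reading the paragraph is told that the chance of missing the primary objective, when there is no true interference, is under 10%. On the inputs given it is over 11%. Second, the paragraph does not say which response rates support its closing claim. The 75% polio assumption is stated just before the calculation but is not used in it, so a reader cannot tell whether the 90% rests on 55% throughout or on separate rates for the two vaccines.

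**Working it through.** **Inputs (Data Analysis and the study-group table).** 800 enrolled per group; 15% loss; margin 0.10; one-sided 0.05 (z = 1.645); true difference zero; response 55% in the power statement; influenza 48–68% and polio as low as 75% in the assumptions list.

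**Completers.** 800 × 0.85 = 680 per group, as the protocol has it.

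**Power per comparison.** Normal approximation with unpooled variance:

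power = Φ(0.10 / √[p(1−p)(1/n1 + 1/n2)] − 1.645)

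- p = 0.55, 680 v 680: standard error = √(0.2475 × 2/680) = 0.02698; 0.10/0.02698 − 1.645 = 2.06; power = 98.04%. The protocol's 98% is reproduced. (The formula asks for 678 per arm for 98%.)

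**Overall power on the protocol's own terms.**

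- As written: 0.98^6 = 0.8858, or 88.6%.
- Unrounded: 0.9804^6 = 0.888, or 88.8%.
- Needed for 90%: 0.90^(1/6) = 0.9826 per comparison, about 699 completers per arm.
- A simulation with 680 per arm, 55% throughout and independent endpoints gave 97.97% per comparison and 88.4% jointly.

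**Overall power with the protocol's separate response rates.**

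- Polio at 75%: standard error = √(0.1875 × 2/680) = 0.02348; power = 99.55%.
- Influenza 55%, polio 75%: 0.9804³ × 0.9955³ = 93.0%.
- Influenza 50% (largest variance within 48–68%), polio 75%: 0.9795³ × 0.9955³ = 92.7%.

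**Sensitivity to the method.** The planned intervals are exact, and their power was not computed. As a rough stand-in, a continuity correction of 1/680 gives:

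| Response rates | Per comparison | All six |
|---|---|---|
| 55% throughout | 97.76% | 0.9776^6 = 87.3% |
| Influenza 55%, polio 75% | 97.76% and 99.46% | 0.9776³ × 0.9946³ = 91.9% |

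**Side calculation on allocation.** Take 4:3:3 with the same 2,400 children: 960/720/720 enrolled, 816/612/612 completers.

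- Variance factor of each primary difference: 1/816 + 1/612 = 0.002859 against 2/680 = 0.002941, a fall of 2.8%.
- Joint power: 88.8% to 90.1% at 55% throughout; 93.0% to 93.8% with polio at 75%.
- Safety, pooled CAIV-T v placebo: (1/1680 + 1/720)/(1/1600 + 1/800) = 1.058, variance up 5.8%.
- Safety, Group 3 v Group 2: (2/720)/(2/800) = 1.11, variance up 11%.
- Safety, Group 1 v Group 2: (1/960 + 1/720)/(2/800) = 0.972, variance down 2.8%.

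**The case against.** **The final claim is right, so the slip does not matter.** This largely stands for the conclusion. With polio at 75%, equal allocation gives about 93%, and a polio rate above 75% would raise it further. It does not rescue the sentence, which derives its figure from six comparisons at 98% and nothing else.

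**The 98% may be rounded down.** Any value from 98.26% upwards would make the sentence true and would still print as 98%. But 680 v 680 at 55% gives 98.04%, and the simulation and the continuity correction both come out lower.

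**Fifteen percent is a ceiling on loss.** At 699 completers per group, a loss of 1 − 699/800 = 12.6%, the product reaches 90%. The protocol, however, ties its 98% to 680. Its immunogenicity population also drops children for dose-interval and blood-draw timing, which adds to loss to follow-up.

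**The six results are not truly independent.** Antigens measured in the same child are likely to be positively correlated, and that raises joint power. With assumed within-child correlations of 0.2 and 0.4, the figure at 55% throughout rises to about 89.4% and 90.2%. The protocol states independence and gives no correlation, so it cannot rely on this as written.

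**A reader might infer that 1:1:1 is the mistake and leaves Group 1 too small**, because Group 1 enters all six comparisons and each reference group only three. The documents do not support that. Group 1 reaches the 680 completers the plan asks for and delivers the stated 98%. The two statements of the ratio agree. The efficiency lost is 0.24 points per comparison (98.04% against 98.27%) and 1.3 points jointly at most. Group 2 is also the only placebo arm, and the safety analysis compares CAIV-T groups with placebo, so moving children out of it has a price.

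**Conclusion.** The overall-power sentence is wrong as written. The correct product is 88.6% (88.8% unrounded), about 1.2 to 1.4 points below the threshold it claims to exceed. This rests on the protocol's own inputs: 680 completers per group, 55% response in every arm and endpoint, no true difference, one-sided 0.05, a 10-point margin and independence.

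It does not follow that the trial is under-powered. On the protocol's own endpoint assumptions (polio 75%, influenza 55% or the least favourable 50%), joint power under equal allocation is 93.0% or 92.7% by the normal approximation. The closing claim of at least 90% can therefore stand once its basis is named, subject to confirmation with the exact interval.

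Nor does it follow that the allocation ratio is an error. A split near 1.4:1:1 is a small efficiency option with a trade-off in safety precision. At 55% throughout, 4:3:3 clears 90% by only 0.1 point on an uncorrected approximation, so it is not a dependable way to make the sentence true.

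**What to change.** In the power paragraph of Data Analysis, replace the overall-probability sentence with one of the following, and state the response rates and the independence assumption:

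- **55% for all six endpoints:** overall power is about 88.6–88.8%. The claim of at least 90% cannot then rest on this calculation.
- **75% for polio and 55% for influenza:** overall power is about 93% (92.7% with influenza at 50%). Give 99.55% per polio comparison and 98.04% per influenza comparison, and say that this is the basis for the claim of at least 90%.

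It would be sensible to confirm the chosen figure with the exact interval that the analysis will use. The cost is a few lines of text and a short calculation. Sample size, randomisation and conduct do not change.

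Optional: if the sponsor wants to look at efficiency before the randomisation list is made, 4:3:3 (960/720/720) lowers the variance of each primary difference by 2.8%. Against that stand 160 more children receiving the combination and the wider safety comparisons shown above. Keeping 1:1:1 needs no correction.

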This is a multi-centre study coordinated and funded by Wyeth Lederle Vaccines. Other proposed sites include Malaysia, India, Philippines, Thailand, Mexico, and Turkey. Overall 2400 participants will be entered into the study, including an estimated 350-400 from Bangladesh. The Bangladesh site will be Kamalapur an urban slum within Dhaka, where ICDDR,B operates a clinic and currently is conducting surveillance and risk factor evaluations for dengue fever and where studies on incidence of acute lower respiratory infections have been conducted.

KEY PERSONNEL (List names of all investigators including PI and their respective specialties)

Name the Project	Professional Discipline/ Specialty	Role in
1. [name]	Epidemiology	Principal Investigator

2. [name]
3. [name]
- 4.

Epidemiology
Epidemiology

Co-principal investigator
Project Manager

DESCRIPTION OF THE RESEARCH PROJECT

Concisely list in order, in the space provided, the hypothesis to be tested and the Specific Aims of the proposed study. Provide the scientific basis of the hypothesis, critically examining the observations leading to the formulation of the hypothesis.

Hypothesis to be tested: Simultaneous administration liquid trivalent cold adapted influenza vaccine and oral polio vaccine will yield antibody levels to both influenza and polio viruses that are not inferior to those produced when the vaccines are given separately.

Specific Aims:

Describe the specific aims of the proposed study. State the specific parameters, biological functions/ rates/ processes that will be assessed by specific methods (TYPE WITHIN LIMITS).

0. To demonstrate that the immune responses to the vaccine influenza viruses, as measured by serum hemagglutination inhibition assay, in children 6 to 36 months of age given influenza virus vaccine, trivalent, types A and B, live, cold-adapted (CAIV-T) concomitantly with a live, attenuated, orally-administered poliovirus vaccine (OPV), are not inferior to those immune responses in children only receiving CAIV-T.
0. To demonstrate that the immune responses to each of the three viruses contained in OPV, as measured by serum neutralisation assay, in children 6 to 36 months of age, given CAIV-T concomitantly with OPV, are not inferior to those immune responses in children only receiving OPV.
0. To assess the safety and tolerability of concomitant administration of CAIV-T with OPV.

Background of the Project including Preliminary Observations

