Each dose of intranasal CAIV-T or placebo will consist of approximately 0.2 ml in total volume administered as an intranasal spray using a spray applicator. Approximately 0.1 ml will be sprayed into each nostril. Details of the specific OPV to be used will be provided in the Investigator manual. OPV will be administered orally according to the manufacturer's instructions. Immediately following the vaccination each subject will be observed for 15 minutes for signs and symptoms of anaphylaxis and local reactions (e.g., nasal congestion/runny nose). The time interval between the assigned first dose and the assigned second dose will be 35 +/- 7 days. Prior to the second vaccination the subject will be assessed for continued eligibility.

A blood sample of approximately 5 millilitres will be collected from subjects on three occasions to evaluate immunogenicity using a serum hemagglutination inhibition assay for influenza virus types A/H1N1, A/H3N2 and B and a virus neutralisation assay for Polio types 1, 2, and 3. These blood samples will be collected prior to the first dose (study visit 1), prior to the second dose (study visit 2), and 35 +/- 7 days after the second dose (study visit 3). Specimen collection and processing guidelines will be provided separate from this document.

Following vaccination, field research assistants (FRAs) will visit each child at home for 11 consecutive days from the day of vaccination, Day 0 to Day 10, and collect data on axillary temperature, runny nose/nasal congestion, cough, vomiting, irritability, and decreases in appetite and activity level using a

standardised questionnaire. The FRA will then check the child's temperature with a digital thermometer supplied by WL.V. If the child has fever, elevated respiratory rate ($> 50/\text{min}$) or danger signs (chest indrawing, lethargy, unwillingness to feed, convulsion, or cyanosis), then the FRA will immediately refer them to clinic. Information regarding any physician consultations and any other concomitant medications (excluding fluoride supplements and vitamins) will also be recorded for 11 days after each vaccination. These children are presently under weekly surveillance for disease incidence (dengue, ALRI, diarrhoea). After the daily visits for 11 consecutive days, routine weekly surveillance will be resumed and all study participants will be advised when to visit the field clinic for their scheduled blood draw on day 35 ± 7 days post vaccination.

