Kamalapur is an urban slum located in the southeastern sector of the Capitol city, Dhaka approximately 30-40 minutes drive from ICDDR,B. The intervention area is spread over 4.0 sq Km (1.5 sq mile or 988 acres) There are 32,339 households in the community, all of which have been entered into an electronic database maintained at ICDDR,B. The total population as of 30 November 2000 was 118,654. The outmigration rate averages < 2%, however the population of the community has doubled since 1997, largely as a result of immigration from rural areas. The population is relatively young. In our 1998 census, the mean age of mean was 32.8 years, of women was 24.2 years, while 11.2% of the population was less than five years old. There is a mixture of squatter settlements and formal permanent structures. The mean household size 4.0 but ranges from 1 - 20 persons per household. Population density is 29,663 per square kilometre (191 persons per acre or 77,048/sq mile). Educational levels in the community among adults are low, however the majority of children less than 12 years attend school. Mean level of schooling for men above 18 years old is 4.5 years, and for women is 3.1 years. Unemployment is relatively low. Most men less than 60 years are employed at least part time, resulting in total unemployment of only 1.6%. Among occupations, the most common for men are merchant (24.2%), office worker (21.6%), rickshaw puller (17.0%), and skilled labourers (12.3%). Day labourers and unskilled workers comprise only 7.7%. (See Figure 1 below.) The mean family income is TK 3,000 or about US \$60/month.

Vaccine coverage for the community is inconsistent and varies by age and type of vaccine. Among the rates of coverage: BCG: 82.8% among children less than 12 months; DPT 1 among 2 month olds = 48.9%; However 81.3% have at least one DPT by 12 months of age; DPT 2 among 4 month olds = 25.2%; DPT 3 among 6 month olds = 65.3%; OPV 1 among 2 month olds = 55.9%; OPV 2 among 4 month olds = 54.4%; OPV 3 among 6 month olds = 97.5%; Measles coverage among children 9 - 12 months old = 45.2%.

Surveillance System

- Active surveillance system, i.e. we actively collect data using a standardised calendar questionnaire.
- Once weekly home visits by a field research assistant (FRA) to every household for data collection.

- The questionnaire asks about specific signs associated with disease for the past seven days since the last visit.
- Those with illness are referred to the field clinic.

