CAIV-T immune response for each virus strain is measured at the end of study by an increase from baseline HAI of four-fold or greater. The primary endpoint for immunogenicity is the proportion of subjects achieving a post-vaccination serum antibody response (as defined above) for each antigen component of OPV and CAIV-T. The primary analysis interval for influenza strains A/H1N1, A/H3N2, and B is one month following the second intranasal vaccination. The primary analysis interval for poliovirus types 1, 2, and 3 is one month following the single dose of OPV.

The secondary endpoint for immunogenicity is the titre of serum antibody for each antigen component of OPV and the titre ratio to baseline of serum antibody to each virus strain of CAIV-T obtained 1 month after vaccination.

The primary analysis interval for influenza strains A/H1N1, A/H3N2, and B is one month following the second intranasal vaccination. The primary analysis interval for poliovirus types 1, 2, and 3 is one month following the single dose of OPV.

The safety objective is to assess the safety and tolerability of CAIV-T in healthy children aged 6 to less than 36 months.

The reactogenicity adverse events are:

Fever (axillary temperature > 37.5°C); Cough; Runny nose or nasal congestion; Irritability; Vomiting; Decreased activity; and Decreased appetite.

The proportion of subjects with any reactogenicity event reported and with other adverse events on any day during the 11-day period following each dose of CAIV-T or placebo will be evaluated. Serious adverse events occurring within 42 days of the first or second vaccination will be listed and summarised.

The overall incidence of reactogenicity events will be compared between the individual CAIV-T groups and the combined Placebo groups using two-sided Fisher's Exact Test. Exact 95% confidence intervals about reactogenicity adverse event frequency differences will be reported. The frequency of other adverse events will be separately compared between subjects randomised to CAIV-T or Placebo using two-sided Fisher's Exact Test.

Ethical Assurance for Protection of Human Rights

Describe in the space provided the justifications for conducting this research in human subjects. If the study needs observations on sick individuals, provide sufficient reasons for using them. Indicate how subject's rights are protected and if there is any benefit or risk to each subject of the study.

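### Diarrhoea is not a solicited Day 0–10 event although two of three groups receive a live oral vaccine at Dose 1, and the planned comparison of unsolicited events does not isolate co-administration

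*Protocol*

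**What the plan says.** The third item under Specific Aims is: "To assess the safety and tolerability of concomitant administration of CAIV-T with OPV". Under Research Design and Methods, Groups 1 and 2 receive OPV at Dose 1 and Group 3 does not. The section on the vaccine to be administered confirms that no oral treatment is given at Visit 2.

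Field research assistants (FRAs) visit daily on Days 0 to 10. They record axillary temperature, "runny nose/nasal congestion, cough, vomiting, irritability, and decreases in appetite and activity level using a" standard form. The reactogenicity events under Data Analysis are fever, cough, runny nose or congestion, and then "Irritability; Vomiting; Decreased activity; and Decreased appetite". Other events are not ignored: "FRAs making daily home visits, as described above, will collect information on adverse events for all subjects". The Study Visit One procedures likewise have FRAs note any other adverse event, unscheduled physician visits and medication.

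On the site's existing surveillance the Protocol says: "These children are presently under weekly surveillance for disease incidence (dengue, ALRI, diarrhoea"). It then adds: "After the daily visits for 11 consecutive days, routine weekly surveillance will be resumed".

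Data Analysis treats the two classes of event differently. Reactogenicity is compared between the individual CAIV-T groups and placebo by Fisher's exact test, with exact 95% intervals for the differences. Other adverse events are compared by Fisher's exact test between children randomised to CAIV-T and those randomised to placebo, with no split by study group.

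**The concern.** The solicited list suits an intranasal vaccine. It was not visibly extended for a trial whose new element is a live vaccine given by mouth at the same visit. The Protocol itself says that no data exist on giving the two together and that no other live virus vaccine has been given within a month of CAIV-T. Tolerability information from this trial would therefore be the first of its kind.

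Two things are at stake. First, an unprompted symptom is recorded less completely than a prompted one. Second, being unsolicited moves diarrhoea out of the group-by-group analysis and into a comparison that mixes children with and without OPV on the CAIV-T side. The trial could then report co-administration as well tolerated without having asked about diarrhoea in any group and without a planned contrast that would show a difference.

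**Working it through.** **Step 1: the two lists side by side.** The daily questionnaire covers temperature, runny nose/congestion, cough, vomiting, irritability, appetite and activity (7 items). The reactogenicity events are fever, cough, runny nose/congestion, irritability, vomiting, decreased activity and decreased appetite (the same 7). Neither has a diarrhoea or stool item. Vomiting is the one clearly gastrointestinal item, or there are two if appetite is counted. Six of the seven, all except appetite, also appear in Table 2, which reports an earlier study of CAIV-T without OPV and has no diarrhoea row.

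**Step 2: where diarrhoea goes instead.** It is recorded as an other adverse event at the daily visits and at the Visit 2 and Visit 3 reviews. It is then analysed as CAIV-T against placebo. By the design table, CAIV-T is Groups 1 and 3 (800 + 800) and placebo is Group 2 (800).

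**Step 3: what that contrast estimates.** Let p1, p2 and p3 be the Day 0–10 diarrhoea proportions after Dose 1. Define e = p1 − p2, the effect of adding CAIV-T to OPV, and d = p2 − p3, the excess of Group 2 over Group 3. With equal groups:

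pooled CAIV-T − placebo = (p1 + p3)/2 − p2 = (p2 + e + p2 − d)/2 − p2 = (e − d)/2.

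The co-administration effect e is halved and then offset by half of d. The Protocol gives no diarrhoea rates, so the values below are assumptions, with p2 held at 15%.

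| d | e | p1 | p3 | Pooled CAIV-T | Pooled − Group 2 | Group 1 − Group 2 |
|---|---|---|---|---|---|---|
| 0 | 0 | 15% | 15% | 15% | 0 | 0 |
| 0 | 5 | 20% | 15% | 17.5% | +2.5 | +5 |
| 2 | 0 | 15% | 13% | 14% | −1 | 0 |
| 2 | 5 | 20% | 13% | 16.5% | +1.5 | +5 |
| 5 | 0 | 15% | 10% | 12.5% | −2.5 | 0 |
| 5 | 5 | 20% | 10% | 15% | 0 | +5 |

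Differences are in percentage points. In the fifth row an excess in the OPV groups appears as lower risk with CAIV-T. In the sixth, a 5-point co-administration effect disappears.

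**Step 4: what soliciting would change.** As a reactogenicity event, diarrhoea would come under the comparison by individual CAIV-T group. Group 1 against Group 2 estimates e directly, both groups receive OPV, and the intranasal assignment is blinded between them. Group 1 against Group 3 would show the effect of adding OPV, but the absence of an oral dose in Group 3 is visible, so that contrast is open to reporting differences.

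**The case against.** The strongest reply is that the Protocol does capture diarrhoea. FRAs collect adverse events daily in every group, parents are told to report significant illness, Visits 2 and 3 review the Day 0–10 events again, and other adverse events are formally tested. No passage names diarrhoea as an expected reaction to OPV, and inclusion already requires three earlier OPV doses. The daily sheets and CRFs come from the company and are not shown, and an analysis plan could break other events down by group. All of this stands. It limits the point to two facts: diarrhoea is unsolicited, and the comparison stated for unsolicited events is a pooled one.

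Several stronger readings are tempting but unsupported:

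- **Surveillance is switched off at vaccination, and that causes the gap.** The pause is only inferred from the statement that weekly visits resume. The weekly form looks back: "The questionnaire asks about specific signs associated with disease for the past seven days since the last visit". The system is described only for the Bangladesh site (350/2,400 to 400/2,400, about 15–17% of children), and Data Analysis does not name it as a safety source. It shows that diarrhoea already matters to the site and no more.
- **Respiratory follow-up is also lost.** It is not. Daily visits record cough and temperature, and if there is fever, raised respiratory rate or "danger signs (chest indrawing, lethargy, unwillingness to feed, convulsion, or cyanosis), then the FRA will immediately refer them to clinic".
- **The problem applies after both doses, or in the only safety window.** OPV is given at Dose 1 only, and serious adverse events are summarised to 42 days after each vaccination.
- **Visible OPV biases the planned co-administration comparison.** It does not bias Group 1 against Group 2, because both groups receive OPV. Group 1 against Group 3 is not a planned safety comparison.

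**Conclusion.** The point holds in a narrow form, as an inexpensive improvement. Diarrhoea is absent from both solicited lists, while a live oral vaccine is given to two of three groups at Dose 1 and tolerability of co-administration is a stated aim. The unsolicited route leads to a comparison that, read literally, estimates (e − d)/2 and not e.

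The algebra rests on equal group sizes and on the literal reading of the pooled comparison. The percentages in the table are assumptions, and the documents do not allow the real size of any effect, or the completeness of unprompted reporting, to be estimated. It would be wrong to conclude that enteric tolerability goes unmeasured. It is measured without a prompt and compared in a way that does not isolate co-administration.

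**What to change.** Add diarrhoea to the Day 0–10 daily questionnaire, both in Research Design and Methods and in the Study Visit procedures, and to the reactogenicity events under Data Analysis. Report its Day 0–10 proportion after Dose 1 for each study group. Give the exact 95% interval already planned for reactogenicity differences for Group 1 against Group 2, and show Group 1 against Group 3 descriptively, noting that it is not blinded for OPV. If diarrhoea is to stay unsolicited, say why.

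The cost is one question at a visit already scheduled, one line on the follow-up sheet and CRF, and one table row. No visits or procedures are added. The drawback is that background diarrhoea will be recorded in all groups. The change has to be made before enrolment, because prompted Day 0–10 data cannot be recovered afterwards.
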